## 8. SAFETY ANALYSIS STRATEGY

Safety analyses will be conducted using the safety population on a treatment-emergent basis.

### 8.1 Safety Endpoints

The safety endpoints are:

- Frequency and Severity of Adverse events.
- Vital Signs (Systolic BP, diastolic BP, pulse rate, oral temperature and respiratory rate)
- Clinical laboratory testing (hematology, clinical chemistry and urinalysis)
- Twelve-lead electrocardiogram (ECG)
- 2D echocardiogram (ECHO)
- Physical Examination.

### 8.2 Safety Hypothesis

There are no formal safety hypotheses in this study. The focus of the safety analysis will be a comprehensive descriptive assessment of the safety endpoints listed in Section 8.1.

### 8.3 Statistical Methods for Safety Analysis

Except otherwise stated, the analysis population for all safety analysis is the safety analysis population as defined in Section 3.2.

#### 8.3.1 Extent of Exposure

Study duration is defined as the date of last visit minus date of informed consent date plus one. Treatment duration is defined as the date of last dose minus the date of the first dose plus one. If the date of last dose is not available, the date of the last visit will be used in the

Document Title:	Statistical Analysis Plan		
Version Number:	1.0	Date:	31 Dec 2021
Protocol Number:	SARO.17.010	Sponsor Name:	Zydus Therapeutics Inc.

calculation. If the date of first dose is not available, the date of baseline visit will be used in the calculation. Study duration and the treatment duration will be summarized descriptively.

Treatment compliance is calculated as the total number of tablets taken divided by the expected number of tablets to be taken during the study period multiplied by 100. Treatment compliance will be summarized descriptively. In addition, a categorical summary of treatment compliance will also be presented using the following categories: < 80%, 80% to 120% and >120%. A patient is considered to be compliant, if he/she takes 80% to 120% of the study drug during the study period.

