### 5.9.1 Discontinuation of Patients from the Study Drug

- Discontinue patient with an AE of CTCAE grade 3 or higher that is possibly or probably related to IP and discontinue patient with an AE of CTCAE grade 4 regardless of attribution to IP.
- 2 If any of the following criteria are met, the patient must be immediately discontinued from IP and followed until resolution of adverse events and laboratory values return to baseline/stable:
  - a. Total Bilirubin ≥3.0 mg/dL.
  - b. Total CK >5 X ULN.
  - c. Amylase or lipase >ULN.
  - d. eGFR <60 mL/min/1.73 m^2 and where the value is reconfirmed after 24 hours repeat. Additionally, any subject who requires renal replacement therapy should also be discontinued from IP.
  - e. Hemoglobin <10 mg/dL or hematocrit <30%; platelets <100,000/ $\mu$ L; WBC <4 x  $10^3/u$ L.
  - f. If troponin and CK-MB exceed the 99th percentile of the upper reference limit of the particular assay, serial labs should be obtained along with serial 12-lead ECGs, and cardiology should be consulted. If a patient has symptoms of dyspnea, edema, or a presumptive diagnosis of heart failure, NT-proBNP should be measured as close to the event as possible.
- 3 The criteria for discontinuing or temporarily interrupting study drug with close monitoring are as follows:
  - a. When the baseline measurements (BLM) are <2x ULN, discontinue if ALT or AST increases to >5x BLM.
  - b. When the BLM ≥2X ULN but <5X ULN, discontinue if ALT or AST increases to >3X BLM.
  - c. When BLM  $\geq$ 5X ULN, discontinue if ALT or AST increases to  $\geq$ 2X BLM.
  - d. For ALT or AST increases to >2X BLM accompanied by a concomitant total bilirubin increase to >2X BLM OR an INR increase by >0.2.

PAGE 39 OF 80

- e. For elevations of liver enzymes accompanied by symptoms consistent with hepatic injury [e.g., fatigue, nausea, vomiting, right upper quadrant pain or tenderness, fever, rash, and/or eosinophilia (>5%)].
- f. Temporarily interrupted treatment should be permanently discontinued for recurrence of laboratory abnormalities or symptoms following re-challenge.
- g. If a patient lives in a remote area, testing can be performed locally and the results communicated to the PI/site promptly.

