#### Visit 8, [Week 24; Day 169 (±3 Days)]

- Concomitant medication will be recorded.
- Dietary assessment will be performed using Diet History Questionnaire (Appendix 2).
- Physical examination, vital signs, body weight measurements, 12-lead ECG, 2D
   ECHO, MRI (Whole Body + PDFF) and MRE will be performed.
- Metabolic flexibility and FSIVGTT will be performed.
- IP bottles will be collected by the PI or designee for checking the compliance.

Approved by:	Protocol No.: SARO.17.010
[name] [name]	Version No.: 7.0

PAGE 55 OF 80

- Safety and efficacy evaluation will be performed as per Table 1 (Schedule of Events), including AE assessment.
- Pharmacokinetic samples will be drawn from applicable patients.
- Serum pregnancy will be performed for female of child-bearing potential.
- Quality of life assessments (SF-36 Health Survey) will be performed.
- Glucometer assessment for diabetic patient.

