### Visit 9, [Week 28; Day 197 (±3 Days)]

- Concomitant medication will be recorded
- Physical examination, vital signs and body weight measurements will be performed.
- Safety parameters will be assessed as per Table 1 (Schedule of Events), including AE assessment.
- Urine pregnancy test will be performed for females of child-bearing potential.
- Glucometer assessment for diabetic patient.

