## 2.2 Study Description

### 2.2.1 Study design

[figure not shown]
This is a Phase 2A prospective, single-center, open-label, single-arm study to evaluate the safety, tolerability and efficacy of Saroglitzazar magnesium 4 mg in liver transplant recipients with non-alcoholic fatty liver disease. Patients who are at least 6 months post-transplant for non-alcoholic steatohepatitis (NASH) or cryptogenic cirrhosis thought to be secondary to NASH are eligible to be enrolled in this study. Approximately 15 male and female patients aged 18 to 75 years who meet the inclusion and exclusion criteria will be enrolled. All eligible patients will receive Saroglitzazar magnesium 4 mg once daily in the morning for a period of 24 weeks.

This study will be conducted over a period of up to 33 weeks and will include a 5-week screening period, a 24-week treatment period and a safety follow-up visit, 4 weeks after the last treatment. The screening period may be extended under special circumstances with the explicit approval of the Sponsors' Medical Expert(s). The study visits will occur at Screening, Baseline (day 1), Week 4 (Day 29 ± 3 days), Week 8 (Day 57 ± 3 days), Week 12 (Day 85 ± 3 days), Week 16 (Day 113 ± 3 days), Week 20 (Day 141 ± 3 days) and Week 24 (Day 169 ± 3 days). A

Document Title:	Statistical Analysis Plan		
Version Number:	1.0	Date:	31 Dec 2021
Protocol Number:	SARO.17.010	Sponsor Name:	Zydus Therapeutics Inc.

[figure not shown]
safety follow-up visit will be conducted approximately 4 weeks after the administration of last dose of the study drug (Day 197 ± 3 days).

Approximately 5 patients will be included in the pharmacokinetic assessment. Pharmacokinetics of Saroglitzazar will be assessed following administration of first (Baseline) and last dose (Week 24). The samples will be collected at Pre-dose (0.0) and 0.5, 1.0, 2.0, 3.0, 4.0, 6.0, 8.0, 10.0 and 24 hours post-dose. In addition, pre-dose sample will be collected at Week 4, 8, 12, 16 and 20 Visits. The study plan is provided below.

Document Title:	Statistical Analysis Plan		
Version Number:	1.0	Date:	31 Dec 2021
Protocol Number:	SARO.17.010	Sponsor Name:	Zydus Therapeutics Inc.

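### SAP 8.3.1 lets the off-drug follow-up visit stand in for a missing last-dose date and counts interruption days as treatment, so the exposure summary can be misstated in either direction

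*SAP*

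**What the plan says.** SAP 8.3.1 (Extent of Exposure) gives two definitions and a fallback:

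- Treatment duration: "Treatment duration is defined as the date of last dose minus the date of the first dose plus one".
- Fallback: "If the date of last dose is not available, the date of the last visit will be used".
- Study duration: "Study duration is defined as the date of last visit minus date of informed consent date plus one". The term last visit therefore marks the end of study participation and includes follow-up.

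On the schedule, SAP 2.2.1 states: "All eligible patients will receive Saroglitzazar magnesium 4 mg once daily in the morning for a period of 24 weeks". It adds that a "safety follow-up visit will be conducted approximately 4 weeks after the administration of last" dose. Protocol 7.2 places Visit 8 (end of treatment) at Day 169 and Visit 9 (follow-up) at Day 197, each ±3 days. Under its unscheduled-visits heading, it asks for Visit 9 procedures when a patient leaves the study early.

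Protocol 5.9.1, item 3, provides for temporary interruption, and item 3f foresees a restart: "Temporarily interrupted treatment should be permanently discontinued for recurrence of laboratory abnormalities or symptoms following re-challenge". The SAP formula subtracts nothing for such periods.

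SAP 8.3.1 also reports tablet-count compliance (tablets taken over tablets expected), both as a continuous summary and in three bands: below 80%, 80% to 120% and above 120%.

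**The concern.** The fallback can produce a treatment duration that the design does not allow: 28 weeks on a drug given for 24. It also mixes two kinds of date. For a patient who attends follow-up, the substituted date is off drug. For a patient who disappears after a dispensing visit, it may be earlier than the true last dose. Separately, a patient whose drug is held and restarted is credited with the days off drug.

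Safety over 24 weeks is the primary objective, and exposure is the context in which adverse events are read. With 15 patients and descriptive summaries only, one wrong value can set the reported maximum and shift the mean.

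**Working it through.** **Inputs.** First dose Day 1, end of treatment Day 169 ±3, follow-up Day 197 ±3 (Protocol 7.2). Drug is dispensed four weeks at a time (Protocol 7.2, Visits 2 to 7). The dose is given on site on scheduled visit days (Protocol 5.2), so a completer's last dose is taken as Day 169. There are 15 patients (SAP 4).

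**1. The plan's own schedule.** (169 − 1)/7 = 24.0 weeks of treatment; 197 − 169 = 28 days = 4 weeks of follow-up; 5 + 24 + 4 = 33 weeks in total. The stated durations reproduce.

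**2. Completer with a missing last-dose date, Visit 9 attended.**
- True duration: 169 − 1 + 1 = 169 days.
- Recorded under the fallback: 197 − 1 + 1 = 197 days.
- Excess: 28 days; 28/169 = 16.6%.
- Smallest excess within the windows: end of treatment Day 172, follow-up Day 194, giving 22 days; 22/172 = 12.8%.
- Largest: end of treatment Day 166, follow-up Day 200, giving 34 days; 34/166 = 20.5%.

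**3. Early stop with a later off-drug visit.** The protocol sets no interval between an early stop and the Visit 9 procedures, so the gap here is an assumption. With 28 days:

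| Last dose | Recorded | Excess |
|---|---|---|
| Day 29 | 57 days | 28/29 = 96.6% |
| Day 57 | 85 days | 28/57 = 49.1% |
| Day 85 | 113 days | 28/85 = 32.9% |
| Day 141 | 169 days | 28/141 = 19.9% |

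**4. Lost to follow-up after an on-drug visit.** Assume that the patient uses the whole new four-week supply, starting on the visit day. Dosing then runs up to 27 days past the visit. With the last visit at Day 85, dosing could reach Day 112, but 85 days are recorded: 27/112 = 24.1% too low.

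**5. Interruptions.** The lengths are assumptions; the first-to-last-dose span is 169 days. Overstatement of on-drug days = g/(169 − g). The SAP does not define the expected number of tablets for interrupted patients; 169 is assumed here.

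| Interruption g | On-drug days | Overstatement | Tablet compliance |
|---|---|---|---|
| 7 | 162 | 7/162 = 4.3% | 162/169 = 95.9% |
| 14 | 155 | 14/155 = 9.0% | 155/169 = 91.7% |
| 28 | 141 | 28/141 = 19.9% | 141/169 = 83.4% |

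All three fall in the 80% to 120% band, so the categorical compliance table would not reveal them.

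**6. Effect on the group mean.** Each completer imputed to Day 197 adds 28/15 = 1.87 days (1.87/169 = 1.1%). Three such patients add 5.6 days (3.3%).

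**The case against.** There are four good arguments in favour of the plan.

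- **The completer case should be rare.** Patients are dosed on site at scheduled visits, bottles are returned and tablets counted (Protocol 5.12 and 7.2, Visit 8), and dispensing is logged (Protocol 5.3 and 9.2.1). A completer's last-dose date should usually be known. This stands: the +28 days needs a missing record, and the documents do not say how often that would happen.
- **The bias is not one-way.** A reader might infer that the substitution always adds off-drug time and that both rules err in the same direction. The documents do not support this. Loss to follow-up is a listed withdrawal reason (Protocol 4.4), and for such a patient the last visit may be on drug, so the fallback can shorten exposure. This removes any claim of general overstatement, but it does not defend the rule, which is then wrong in both directions.
- **The span definition is openly stated, and compliance is reported beside it.** The continuous compliance summary does pick up missed tablets. However, its denominator is undefined for interrupted or stopped patients, and a four-week gap can still count as compliant.
- **Nothing downstream uses treatment duration.** The treatment-emergent window runs from first exposure to study exit (SAP 8.3.2), adverse events are summarised as counts and percentages, and no exposure-adjusted rates or safety hypotheses are planned. This stands in full and limits the importance of the point.

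**Conclusion.** The point holds as a minor one. The fallback is a stated rule without a cap, and for any patient who attends the off-drug follow-up visit it counts off-drug days as treatment: 197 instead of 169 days for a completer (+16.6%, range 12.8% to 20.5% with the visit windows). For a patient lost after an on-drug visit it can understate by up to 27 days. Interruption days are credited as treatment, by 4.3% to 19.9% for assumed gaps of 7 to 28 days.

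These sizes apply only to patients with a missing last-dose date or an interruption. The interruption lengths, the 28-day gap after an early stop, the full use of a last supply and the 169-tablet denominator are assumptions.

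A reader might also infer that the primary safety result is biased. The documents do not support that: only the descriptive exposure summary changes.

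**What to change.** Amend SAP 8.3.1 as follows.

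1. When the last-dose date is missing, use the recorded treatment-stop date if there is one.
2. If there is none, use the last date supported by drug-accountability records; failing that, the last on-treatment visit. The imputed date is never later than the end-of-treatment visit and never the follow-up visit.
3. Report treatment duration net of documented interruption days beside the first-to-last-dose span.
4. Define the expected number of tablets for interrupted and discontinued patients.

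The order in steps 1 and 2 matters. Taking the earlier of the stop date and the last on-treatment visit would discard a known date. With a recorded stop at Day 110 and a last on-treatment visit at Day 85, it would give 85 days, 25/110 = 23% too few.

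The cost is a few SAP sentences and a small derivation change. No new data are needed, because the rules use only recorded stop dates, accountability records and documented interruptions.

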### 8.3.2 Adverse Events

The applicable definition of an Adverse Event (AE) is in the study protocol section 9.4. A treatment-emergent AE (TEAE) is an event not present prior to exposure to study drug or any pre-existing event that worsens following exposure to study drug. The period for treatment-emergent AE analysis starts from the first exposure to the study drug until the patient exits the study.

Descriptive summaries (frequencies and percentages) for specific TEAEs will be presented by system organ class and preferred term according to the Medical Dictionary for Regulatory Activities (MedDRA Version 21.0) dictionary. In addition to an overall presentation of all TEAEs, reports will be generated for special classes of TEAEs such as drug related TEAEs, serious TEAEs, Maximum severity and TEAEs resulting in treatment discontinuation. These reports will be supported by individual patient listings, as necessary.

Adverse events will be counted by the number of events as well as the number of patients. For the summaries which count the number of patients, multiple TEAEs with the same MedDRA preferred term within the same patient will only be counted once.

Only patient listings will be provided for AEs that occur after signing informed consent but prior to exposure to study drug. These listings will comprise all events occurring during this period in any patient who consented to participate in the study.

These listings will at least contain but not limited to information such as onset and resolution times, maximum severity, causal relationship to study drug and action taken.

Statistical Analysis Plan			
Version Number:	1.0	Date:	31 Dec 2021
Protocol Number:	SARO.17.010	Sponsor Name:	Zydus Therapeutics Inc.

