Pharmacokinetics of Saroglitazar will be assessed following first dose and last dose in liver transplant recipients with NAFLD. The samples will be collected at Pre-dose (0.0), 0.5, 1.0, 2.0, 3.0, 4.0, 6.0, 8.0, 10.0 and 24 hours post-dose. In addition, pre-dose sample will be collected at Visits 3, 4, 5, 6 and 7.

At the End of Treatment visit, all required parameters and assessments will be performed again.

Subjects will return for their final visit, the Follow-up visit, 4-week after the last dose of the study drug. At this visit assessments include a targeted physical examination (lab results/signs/symptom driven), vital signs, safety laboratory tests, a review of concomitant medications and AEs. A urine pregnancy test will be performed for females of child bearing potential only. All the study related procedures will be performed as per table 1 (Schedule of Events).

Unscheduled visits – Permitted at any time during the study for assessment and management of AEs and any concurrent clinical conditions. To be captured in the electronic case report form (eCRF).

• If further investigations are required in case of any AEs, PI will assess the AE and take necessary action, if required.

Approved by: Protocol No.: SARO.17.010
[name] [name] Version No.: 7.0

Confidential Page 8 of 80

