### 4.4 WITHDRAWAL CRITERIA

The Investigator may withdraw a subject from the study for any of the following:

- 1 Subject who reports an SAE and if considered in Investigator or Medical Expert's opinion it is not in the subject's best interest to continue.
- 2 Any subject found to have entered the study in violation of the protocol.
- 3 Termination of the study by the Sponsor or Principal Investigator (PI) or the regulatory authorities or Independent Ethics Committee/Institutional Review Board (IEC/IRB).
- 4 The subject is lost to follow-up.
- 5 Any subject who wishes to withdraw his/her consent for participation in the study.
- 6 In case a subject becomes pregnant, then she will be withdrawn from the study.

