### 4.5 HANDLING OF SUBJECT WITHDRAWAL

In case of withdrawal of consent, and unless otherwise stated by the subject in the withdrawal of consent, PI(s) will be encouraged to obtain information from the subject in order to follow the medical status of the subjects (especially when the subject withdraws his/her consent after having experienced an AE/SAE or an efficacy endpoint). Principal Investigator or designee(s) must make reasonable attempts (at least 3 attempts, one of which will be via a certified/traceable mail) to contact subjects that are lost to follow-up, in order to obtain health status and reason for withdrawal. These attempts must be documented in the medical records. In addition, if patient withdraws from the study, any data collected during the period of time will maintained as part of the study data.

Approved by: [name] [name] Protocol No.: SARO.17.010

CONFIDENTIAL
PAGE 33 OF 80

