#### 6.1.5 Adverse events

Adverse event reporting will begin after the informed consent has been signed and will continue until end of follow-up period. The Common Terminology Criteria for Adverse Event (CTCAE) (Version 4.03 or higher) system will be used for reporting and grading AEs. Please refer Section 9.4 for details description.

All AEs will be captured in the AE eCRF. At a minimum, SAEs will be reported in the eCRFs as per the timelines defined in the Protocol in adverse event section.

Serious adverse events reporting must comply with the concerned regulatory requirements and IEC/IRB reporting requirements.

Approved by:	Protocol No.: SARO.17.010
[name] [name]	Version No.: 7.0

CONFIDENTIAL

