#### **Unscheduled visits**

Unscheduled visits are permitted at any time during the study at the discretion of the PI or designee for assessment and management of AEs and any concurrent clinical conditions, Data will be captured in the eCRF.

If further investigations are required in case of any AE, PI will assess the AE and take necessary action, as required.

Immunosuppression levels will be monitored on Day -1, Day 1, Day 3, Day 7 and Weekly (Days 14, 21 and 28) for first month. If the Immunosuppression levels remain stable as per the opinion of the transplant hepatologist, they will then be monitored on a monthly basis (Days 57, 85, 113, 141 and 169) until the end of the study or as per the opinion of the transplant hepatologist/study investigator for clinical care.

If due to any reason after randomization, the patient discontinues the study before the End of Study Visit, all procedures of End of Study Visit (Visit 9) should be carried out.

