#### Serious Adverse Event Reporting-Procedures for Investigator:

#### **Initial Reports:**

Any SAE, or follow-up to a SAE, including death due to any cause that occurs to any subject from the time the consent is signed through 4-week following cessation of treatment, whether or not related to the Sponsor's product, must be reported to the Sponsor within 24 hours of the knowledge of the occurrence to investigational site.

Additionally, any SAE, considered by the PI or designee, who is a qualified physician, to be related to the Sponsor's product, that is brought to the attention of the PI or designee at any

[figure not shown]

CONFIDENTIAL PAGE 68 OF 80

time outside of the time-period specified in the previous paragraph also must be reported immediately to the Sponsor.

To report an SAE, complete the SAE form electronically in the electronic data capture (EDC) system for the study. Once the form is completed, the CRO/Sponsor Safety personnel will be notified electronically. If the event meets serious criteria, and, it is not possible to access the EDC system, send an email to CRO/Sponsor or call the CRO/Sponsor SAE hotline (phone number listed below), and email the completed SAE form/information to CRO/Sponsor (email listed below) within 24 hours of awareness. When the EDC system becomes available, the SAE information must be entered within 24 hours of the system becoming available.

Safety Contact Information:

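### The treatment-emergent period ends at study exit, so an SAE or death reportable within 4 weeks of the last dose may go uncounted in a patient who leaves early

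*SAP*

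**What the plan says.** SAP 8.3.2 sets the analysis window for treatment-emergent events: "The period for treatment-emergent AE analysis starts from the first exposure to the study drug until the patient exits the study". Neither that section nor any other readable part of the SAP defines exit or gives a number of days after the last dose. The nearest anchor is SAP 8.3.1, which ends study duration at the last visit. SAP 8 puts the safety analyses on a treatment-emergent basis. The only listing that SAP 8.3.2 promises specifically for events that are not treatment-emergent covers those between consent and first dose.

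Protocol 9.4.2 sets a window tied to dosing. The investigator must report every SAE, drug-related or not, and the scope is given as follows: "including death due to any cause that occurs to any subject from the time the consent is signed through 4-week following cessation of treatment". Protocol 6.1.5 covers adverse events in general: "Adverse event reporting will begin after the informed consent has been signed and will continue until end of follow-up period".

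For the planned course, the protocol summary says "Subjects will return for their final visit, the Follow-up visit, 4-week after the last dose of the study drug". For early leavers, the unscheduled-visits text in Protocol 7.2 says that if "the patient discontinues the study before the End of Study Visit, all procedures of End of Study Visit (Visit 9) should be carried out". It does not say when, relative to the last dose.

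Protocol 4.4 lists loss to follow-up as a ground for withdrawal, and also "Any subject who wishes to withdraw his/her consent for participation in the study". Protocol 4.5 expects some information after such an exit. After consent withdrawal, unless the patient has said otherwise, "PI(s) will be encouraged to obtain information from the subject in order to follow the medical status of the subjects". At least three attempts must be made "to contact subjects that are lost to follow-up, in order to obtain health status and reason for withdrawal".

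**The concern.** The reporting window is counted from the last dose and the analysis window from leaving the study. The two coincide for a patient who follows the schedule. They can separate for one who stops drug and leaves soon afterwards. In that patient, an SAE that begins after exit but within 4 weeks of the last dose has to be reported to the sponsor, yet on the most natural reading of exit it lies outside the window from which the TEAE tables are built.

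Safety is the primary endpoint, and Protocol 8.2.2 summarises adverse events by counts and percentages. With 15 patients, one missing patient is visible in those tables. A serious-TEAE row showing zero when an SAE had been reported 10 days after the last dose would be an awkward result to explain.

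**Working it through.** The plan has no figure of its own to reproduce: no power calculation, margin or event target depends on this point.

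**Inputs**
- Reporting window: 4 weeks = 28 days after treatment stops (Protocol 9.4.2).
- Visit 8: Day 169 ± 3. Visit 9: Day 197 ± 3 (Protocol 7.2).
- Sample size: 15 (SAP 4).
- Assumptions: the last dose of a completer is on the day of Visit 8, and exit is the last visit or the withdrawal date.

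**Length of the gap**

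Uncovered days = max(0, last-dose day + 28 − exit day).

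| Patient | Last dose | Exit | Uncovered days |
|---|---|---|---|
| Completer on schedule | Day 169 | Day 197 | 169 + 28 − 197 = 0 |
| Completer, Visit 9 early | Day 169 | Day 194 | 169 + 28 − 194 = 3 |
| Completer, opposite window extremes | Day 172 | Day 194 | 172 + 28 − 194 = 6 |
| Leaves on the day of the last dose | Day 85 (example) | Day 85 | 85 + 28 − 85 = 28 |
| Leaves 14 days after the last dose | Day d | Day d + 14 | 28 − 14 = 14 |
| Stops drug, stays until 28 days or more after the last dose | Day d | Day d + 28 or later | 0 |

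**Effect of one omitted patient**

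1/15 = 6.7%. If the patient had no other serious TEAE, the table would show 0/15 (exact Clopper-Pearson 95% interval 0 to 21.8%) instead of 1/15 = 6.7% (0.2 to 31.9%). The intervals only give scale. SAP 8.3.2 plans frequencies and percentages.

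**Chance of an omission**

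The documents give neither a withdrawal rate nor an SAE rate, so this is illustration only. With k early leavers who all exit on the day of the last dose, and r new-onset SAEs per patient-year, P = 1 − exp(−k × r × 28/365.25).
- k = 1, r = 0.1: 0.8%
- k = 3, r = 0.3: 6.7%
- k = 5, r = 0.5: 17.4%

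All k and r values are assumed. For given k and r, each result is an upper bound, because it supposes immediate exit and that every such event becomes known to the site. The last line needs a third of the patients to leave on their last-dose day.

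**Does other text close the gap?**
- The TEAE definition in SAP 8.3.2 has no end date, but the window sentence that follows limits the analysis period.
- Protocol 8.2.2 has all adverse events in the study period listed and summarised. Study period is not defined there either, and SAP 1 lets the SAP prevail where the two differ.
- SAP 6.1 treats events with completely missing dates as treatment-emergent, and those with partial dates too unless the known part rules it out. Poorly dated second-hand reports would therefore often be counted. A fully dated event after exit would not.

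**The case against.** The strongest defence is that exit has a natural meaning. SAP 8.3.1 ends study duration at the last visit, and Protocol 7.2 calls Visit 9 the End of Study Visit. Protocol 9.2.3 has the site record the conclusion of each patient's participation. This stands, and it answers one tempting inference, that exit would be chosen freely once the events are known. It does not close the gap: last visit is the very reading under which an early leaver's window can end before 28 days.

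A reader might also infer that completers lose their follow-up events, because SAP 3.1 links completion to the Week 24 assessment. The documents do not support that. The phrase is a criterion for the per-protocol population, and SAP 2.2.1 places the 4-week follow-up visit inside the study.

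Other points stand as limits:
- Stopping drug is not leaving the study. Protocol 5.9.1 follows patients who stop for the listed laboratory criteria.
- If an early leaver's Visit 9 is held 4 weeks after the last dose, there is no gap. The schedule of events in the protocol and the study plan in SAP 2.2.2 could not be read in the text available, so a timing rule there cannot be excluded.
- After consent withdrawal, seeking information is only encouraged, so some events would never become known.
- A reporting window and an analysis window need not be equal. But when the reports are already compulsory and safety is the primary endpoint, leaving them out of the counts needs a reason, and none is given.

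**Conclusion.** The point holds as a low-severity gap in the SAP. If exit is the last visit or the withdrawal date, a fully dated SAE or death that begins after exit and within 28 days of the last dose is reportable under Protocol 9.4.2 but not counted as a TEAE. The exposure is up to 28 days per early leaver, nominally 0 for completers and for those who stay through Visit 9, and at most 6 days at the visit-window extremes. One omitted patient is 6.7 percentage points.

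The documents do not support saying that such events will be dropped. That depends on how exit is read, on when Visit 9 is held for early leavers, and on whether the site learns of the event. Nor would the event necessarily vanish from the report: the statement in Protocol 8.2.2 on all adverse events may bring it in. An SAE that began before exit and later proves fatal stays counted. The stopping and monitoring triggers in Protocol 5.9 and 7.5 do not use this window, and no overall conclusion would be reversed.

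**What to change.** In SAP 8.3.2, define the treatment-emergent period as first dose through the later of study exit and 28 days after the last dose. Define study exit there as the date of the last visit or the recorded conclusion of participation, and say which applies when they differ. Add one listing of all deaths and SAEs whatever their treatment-emergent flag, with study day and days since last dose. The gap is then 0 days for every patient.

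The cost is a change of SAP wording, one listing and a table footnote. No visits or data collection are added, because Protocol 9.4.2 already requires these reports. The small downside is that, after exit, mainly SAEs rather than ordinary adverse events will be captured. The footnote should say so.
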